6.3.2. Caffeine, Alcohol, and Tobacco

Consumption of caffeine- and xanthine-containing products is allowed, provided that the subject's consumption has been consistent for the last 30 days and will remain consistent throughout the duration of the study.

Subjects will not be permitted to consume alcohol from 48 hours prior to CRU admissions and while resident at the CRU. During the study, while not resident at the CRU, the maximum daily alcohol intake should not exceed 2 units (see Exclusion Criterion [27], Section [6.2](#), for unit definition).

Smoking, tobacco consumption, or use of any nicotine-replacement therapy is not permitted while resident at the CRU. While not resident in the CRU, smoking should not exceed 10 cigarettes per day or equivalent in nicotine use or nicotine substitutes.

6.3.3. Activity

Subjects should avoid strenuous exercise and/or activity for at least 48 hours prior to CRU admission and while resident at the CRU.

Subjects should remain upright for at least 2 hours after dosing, with the exception of any requirements for protocol procedures (eg, supine for ECGs).

6.3.4. Blood and Plasma Donations

Subjects are not permitted to make blood or plasma donations while participating in the study.

6.4. Screen Failures

As this study will be conducted in healthy subjects only, individuals who do not meet the criteria for participation (ie, screen failure) may not be re-screened, although specific tests such as clinical laboratory tests and vital signs/ECGs may be repeated at the discretion of the investigator to confirm study eligibility.

Subjects who were eligible for inclusion in previous cohorts but were not randomized for nonmedical reasons may be reassessed for eligibility/inclusion in a subsequent cohort.

7. Treatment

7.1. Treatment Administered

This study involves a comparison of LY3154885 or matching placebo administered orally. [Table HUAA.7.1](#) shows the treatment regimens.

Capsules (or tablets for optional Part D) of LY3154885 and/or placebo will be administered orally with approximately 240 mL of room temperature water in the morning of each dosing day with subjects in a sitting position. Subjects will not be allowed to lie supine for approximately 2 hours after dosing, unless clinically indicated or for study procedures.

Table HUAA.7.1. Treatments Administered

Treatment Name	LY3154885	LY3154885	Placebo	Itraconazole
Dosage Formulation	Capsule	Tablet	Capsule	Solution
Unit Dose Strength(s)/ Dosage Level(s)	Extemporaneous preparation 15 to 500 mg	Extemporaneous preparation Dose to be determined	Matching placebo	10 mg/mL
Route of Administration	Oral	Oral	Oral	Oral

The investigator or designee is responsible for:

- explaining the correct use of the investigational product(s) to the subject
- verifying that instructions are followed properly
- maintaining accurate records of investigational product dispensing and collection
- returning all unused medication to Lilly or its designee at the end of the study

Note: In some cases, sites may destroy the material if, during the investigative site selection, the evaluator has verified and documented that the site has appropriate facilities and written procedures to dispose of clinical materials.

7.1.1. Packaging and Labeling

The LY3154885 capsules or tablets will be prepared extemporaneously. The proposed range of strengths to be prepared is listed in [Table HUAA.7.1](#).

In Parts A, B and C, for any specific cohort/dosing period, the total number of capsules administered will be the same for all subjects, regardless of whether assigned to placebo or LY3154885. However, the number of capsules may vary between dosing periods and cohorts to maintain the blind.

Instructions for extemporaneous preparation of the study drug will be provided by the sponsor. This will be performed by trained personnel (eg, pharmacist) within a facility at the CRU who are qualified to perform these types of operations.

For LY3154885 capsules, the LY3154885 pure compound with no inactive ingredients will be filled into capsules.

For LY3154885 tablets, the LY3154885 pure compound will be combined with other common excipients and compressed into tablets for use in Part D.

Matching placebo for the LY3154885 capsules will be sourced centrally. Itraconazole will be sourced locally by the site.

The investigational product will be labeled according to the country's regulatory requirements.

7.2. Method of Treatment Assignment

In Parts A, B, and C, the randomization table will be prepared by the statistician (or appropriate delegate) for the study and provided to the CRU pharmacists or pharmacy staff involved in dose preparation. The allocation and dispensing of the study drug will be fully documented and verified by a second person. Detailed records of the amounts of the study drug received, prepared, dispensed, and remaining at the end of the study will be maintained by the CRU pharmacist.

7.2.1. Selection and Timing of Doses

The doses will be administered at approximately the same times on each day. The actual time of all dose administrations will be recorded in the subject's case report form (CRF). In Part B, for the outpatient dosing days for itraconazole, subjects will record the actual time of dose administration on a diary card.

Dosing with itraconazole should occur approximately 1 hour before dosing with LY3154885 (or placebo) when the 2 drugs are coadministered.

7.3. Blinding

Parts A, B, and C will be investigator- and subject-blind; Part D will be open-label. The sponsors and site monitors are not blinded.

To preserve the blind, only a minimum number of personnel at the CRU (namely, CRU pharmacy staff) will see the randomization table before the study is complete. Individuals involved with study drug preparation will not be involved in any of the clinical aspects of the study, including study drug administration and AE assessments. Blinding will be maintained throughout the conduct of the study until after all data are cleaned to an acceptable level of quality and the CRF is entry locked.

In case of an emergency, the investigator has the sole responsibility for determining if unblinding of a subject's treatment assignment is warranted for medical management of the event. The subject's safety must always be the first consideration in making such a determination. If the investigator decides that unblinding is warranted, it is the responsibility of the investigator to promptly document the decision and rationale and notify Lilly as soon as possible.

Upon completion of the study, all codes must be returned to Lilly or its designee.

7.4. Dose Modification

Dose levels, sampling schedule, timing of procedures (eg, PK and ECG assessments), and length of CRU stay may be adjusted in view of emerging safety or PK data during the study. Dose increments may be changed, a dose level may be repeated, or a lower dose may be administered. If a dose reduction is required, the dose level for the following cohort (ie, the cohort following the one that received a lower than planned dose) cannot exceed $\frac{1}{2}$ log. The timing of blood samplings may be adjusted, but the number of samples will not exceed what has been planned, plus the additional samples. The duration of the CRU stay or the duration of safety follow-up may be increased (eg, if the half-life of LY3154885 is longer than anticipated) but not decreased. These changes must be appropriately documented and communicated by the sponsor to the investigator. Because these adjustments to timings or dose levels are allowable changes permitted by the protocol, they would not require a protocol amendment.

7.4.1. Dose Decision/Escalation

By nature of being a dose-escalation study, data will be evaluated on an ongoing basis until the maximum tolerated dose (MTD) is determined or the highest planned dose is administered. The highest dose level that is tolerated will be designated as the MTD.

Safety data will be the primary criteria for the dose escalation. In addition, if available at the time of the dose-escalation decision, PK results will be used as supporting data. No dose escalation can occur without prior discussion and agreement between the investigator and the Lilly study team. See Sections 5.1.1 and 5.1.3 for further details.

Safety data, in particular AEs, SAEs, BP, PR, and adverse laboratory abnormalities, will be independently assessed by the investigator and will be considered related to the investigational medicinal product, unless there is clear evidence that the event is not related.

If any of the following scenarios occur, dosing at the current level and further dose escalation will be discontinued:

- 1) a single subject experiences an SAE that is related to LY3154885 administration
- 2) 2 subjects experience a clinically significant event of persistent tremors that is deemed to be related to LY3154885 administration
- 3) 2 subjects experience clinically significant increases in scheduled vital signs that are deemed to be related to LY3154885 administration
- 4) 2 or more subjects at 1 dose level experience other moderate or severe treatment-related AEs that impair normal activities and are deemed to be related to LY3154885 administration

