3.1. Study Rationale

LY3154885 has not been administered to humans. This first-in-human study will investigate the safety, tolerability, and pharmacokinetics (PK) of single and multiple doses of LY3154885 in healthy subjects. The study will also investigate the impact of cytochrome P450 (CYP) 3A4 inhibition on the safety, tolerability, and PK of LY3154885 after a single dose via a tablet or capsule formulation. The data generated in this study will be used to help design subsequent clinical studies.

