5.5. Justification for Dose

In Part A, the planned clinical doses to be tested are 15, 45, 100, 200, 400, and 500 mg based on animal toxicology/toxicokinetics, preclinical pharmacology, and PK information. In Part B (CYP3A4 Interaction), the LY3154885 dose selection will be based on emerging data from Part A but is currently planned to be \leq 200 mg. In Part C (MAD), dose selection will be based on emerging safety, tolerability, and PK data from Part A and Part B, but Part C is currently planned to start at 35 mg and not exceed the highest dose in Part A or the maximum exposure achieved in Part A or B that are found to be well tolerated. In Part D, the dose for the capsule and tablet is planned to be \leq 400 mg but will ultimately be based on emerging safety, tolerability, and PK data from Part A.

The toxicity profile of LY3154885 has been characterized in rats and monkeys through a package of GLP compliant, repeat-dose toxicology, safety pharmacology, and genetic toxicology studies; non-GLP toxicity studies were conducted with LY3154885 as well and are discussed in the IB. These studies with LY3154885 demonstrate an acceptable safety profile for human testing with CV and CNS effects that are transient and monitorable.

CCI

CCI

(Table HUAA.5.1).

The maximum dose for this study is expected to be 500 mg based on animal toxicology studies and human PK predictions for LY3154885, CCI

CCI A 500-mg dose in humans is predicted to result in a mean plasma AUC of CCI $\mu\text{g}\cdot\text{hr}/\text{mL}$ and C_{\max} of CCI $\mu\text{g}/\text{mL}$; these values are equivalent to 1/10th the AUC at the NOAEL in monkeys and 1/10th the C_{\max} at the NOAEL in rats. The C_{\max} and AUC-based multiples associated with CCI from the non-GLP study in rats, which were not observed at similar exposures in the GLP study, are also presented in Table HUAA.5.1. To note, the predicted human C_{\max} at 500 mg is CCI below the C_{\max} at the NOEL for PPD in both rats and monkeys. Pharmacokinetic data will be reviewed during the study to support dose escalations (see Section 10.3.5 for details) and maintain predicted drug exposures below 1/10th the AUC at the NOAEL in monkeys and 1/10th the C_{\max} at the NOAEL in rats. A dose higher than 500 mg may be studied if human PK data from previous cohorts suggests the predicted exposure will be below 1/10th the AUC at the NOAEL in monkeys and 1/10th the C_{\max} at the NOAEL in rats.

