In Part B (CYP3A4 Interaction), the LY3154885 dose selection will be based on emerging data from Part A but is currently planned to be ≤ 200 mg. It is predicted that the maximum exposure increase in LY3154885 when administered with itraconazole, a strong CYP3A4 inhibitor, is

approximately 2.6-fold. Therefore, the LY3154885 dose selected will be below the highest dose deemed well tolerated that has a plasma exposure to allow for up to a 2.6-fold increase in exposure that may result from coadministration with itraconazole, and the predicted LY3154885 plasma exposure at this dose when coadministered with itraconazole will be below 1/10th the AUC at the NOAEL in monkeys and 1/10th the C_{max} at the NOAEL in rats. The dose regimen for itraconazole will be 200 mg twice daily on Day 8 (dose separated by 12 hours) and once daily on Days 9 through 17.

[figure not shown]
In Part C (MAD), the doses will be based on emerging safety, tolerability, and PK data from Part A (SAD) and Part B. Emerging safety and tolerability data from Part C will also be considered for dose escalation. The highest dose tested in Part C will not exceed the highest dose in Part A (currently planned to be 500 mg) that was well tolerated or the maximum exposure achieved in Part A or B found to be well tolerated.

In Part D, the planned dose for the capsule and tablet will be ≤ 400 mg but will ultimately be based on emerging safety, tolerability, and PK data from Part A.

CCI

CCI

6. Study Population

Eligibility of subjects for the study will be based on the results of screening medical history, physical examination, vital signs, clinical laboratory tests, and ECG. The nature of any conditions present at the time of the physical examination and any preexisting conditions will be documented.

Screening may occur up to 28 days prior to enrollment. Subjects who are not enrolled within 28 days of screening may be subjected to an additional medical assessment and/or clinical measurements to confirm their eligibility.

Prospective approval of protocol deviations to recruitment and enrollment criteria, also known as protocol waivers or exemptions, are not permitted.

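### Section 7.4.1 designates the highest tolerated dose as the MTD without requiring that a higher dose was given and not tolerated, so a tolerated top dose would be named an MTD that was not reached

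*Protocol*

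**What the plan says.** Protocol Section 7.4.1 describes escalation as continuing "until the maximum tolerated dose (MTD) is determined or the highest planned dose is administered". It then gives the naming rule: "The highest dose level that is tolerated will be designated as the MTD". For detail it adds "See Sections 5.1.1 and 5.1.3 for further details", which points to Part A (single dose) and Part C (14 days of dosing), yet it speaks of one MTD.

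Section 5.5 gives the basis of the Part A top dose: "The maximum dose for this study is expected to be 500 mg based on animal toxicology studies and human PK predictions". It allows a dose above 500 mg only if predicted exposure stays under one tenth of the NOAEL exposures (AUC in monkeys, Cmax in rats). For Part C it says "The highest dose tested in Part C will not exceed the highest dose in Part A (currently planned to be 500 mg"), qualified as a dose that was well tolerated, with the highest well-tolerated exposure in Part A or B as a further limit.

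Appendix 1 of the protocol spells out the abbreviation MTD without defining it. The SAP does not contain the term.

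**The concern.** The two sentences in Section 7.4.1 do not fit together. The first separates finding an MTD from running out of planned doses. The second names an MTD whichever of these happened. A maximum tolerated dose is informative because something above it was not tolerated. Without that condition, the label can be attached to a dose at which escalation stopped for a reason unrelated to tolerability.

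What is at stake is how the tolerability result is described to those who use it later. Section 3.1 says "The data generated in this study will be used to help design subsequent clinical studies". A reader told that 500 mg is the MTD would take it that tolerability limits dosing there, when the study might have shown only that 500 mg was tolerated and nothing higher was tried.

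**Working it through.** The plan gives no figure for this rule, so there is none to reproduce. The check applies the designation sentence to each way escalation can end.

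**Inputs.** Part A doses: 15, 45, 100, 200, 400 and 500 mg (Section 5.1.1). Basis of the 500 mg maximum and the exposure limits: Section 5.5. PK reviews before Dose 5 and before Dose 6: Section 10.3.5. Dose levels may be changed in view of emerging safety or PK data: Section 7.4. Part C: up to 3 dose levels (Section 5.1.3).

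| Course of escalation | Dose not tolerated? | Rule as written gives | Supported conclusion |
|---|---|---|---|
| Part A: 200 mg tolerated, 400 mg not | Yes, 400 mg | MTD 200 mg | MTD 200 mg |
| Part A: 400 mg tolerated, 500 mg not | Yes, 500 mg | MTD 400 mg | MTD 400 mg |
| Part A: all doses to 500 mg tolerated | None | MTD 500 mg | Not reached; 500 mg tolerated |
| Part A: PK review ends escalation after a tolerated 400 mg | None | MTD 400 mg | Not reached; 400 mg tolerated, stopped for exposure |
| Part C: top dose given and tolerated | None | MTD = top Part C dose | Not reached for multiple dosing |

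The second row shows that giving the highest planned dose is not itself the problem: if that dose is not tolerated, the rule works. It fails when no dose was found not tolerated.

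The fourth row follows from the plan's own limits. Section 5.5 puts predicted exposure at 500 mg level with one tenth of the NOAEL values, and says PK will be reviewed to keep predicted exposure below them. If Part A exposures run higher than predicted, the reviews before Dose 5 (400 mg) or Dose 6 (500 mg) could end escalation at a tolerated lower dose.

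A dose above 500 mg does not alter the reasoning. Escalation has then not ended, and the same question arises at the new top dose.

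**Illustration of whether the affected case is remote.** Section 5.1.1 intends 8 subjects on active drug per Part A dose. The fourth stopping scenario in Section 7.4.1 needs "2 or more subjects at 1 dose level experience other moderate or severe treatment-related AEs" that impair normal activities. If each subject independently has such an event with probability p, the chance that it does not trigger at a given dose is (1 − p)^8 + 8p(1 − p)^7:

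- p = 0.05: 0.663 + 0.279 = 0.94
- p = 0.10: 0.430 + 0.383 = 0.81
- p = 0.20: 0.168 + 0.336 = 0.50
- p = 0.30: 0.058 + 0.198 = 0.26

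The values of p are assumptions; the documents give none. Only this scenario is modelled, and not triggering it is not the same as being tolerated. The figures show only that passing the top dose without this stop is an ordinary outcome over a wide range of event rates. They are not a probability of mislabelling.

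**The case against.** The strongest reply is that the first sentence already carries the distinction. Its two alternatives allow the study to end without an MTD, and the next sentence can be read as saying what the MTD is when the first ending occurs. That reading is sensible and probably intended. It needs a condition that the designation sentence does not contain, though, and neither Appendix 1 nor the SAP supplies it.

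A second reply is that nothing depends on the label. This stands, and it limits the point. MTD is not an objective or endpoint. The Part B, C and D dose limits are written in terms of doses or exposures that were well tolerated, so a reader who infers that participants could be dosed wrongly because of this sentence would be mistaken.

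Third, a reader might infer that the top dose is purely an exposure cap in both parts. That fits the expected 500 mg in Part A. It does not fit Part C, whose ceiling depends on what was well tolerated earlier. The Part C problem is narrower: if its own top dose is tolerated for 14 days, no multiple-dose MTD has been found, whatever set the ceiling.

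Fourth, the protocol says designated, not reported. Neither document specifies a table or endpoint that presents an MTD. That the label would appear in the study report is a reasonable inference, but it remains an inference.

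**Conclusion.** The sentence is wrong as written. If every dose given is tolerated, it names an MTD that was not reached. This applies to Part A at 500 mg, or at a lower dose after a PK-driven stop, and to Part C at its top dose.

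The size is minor. Only the designated tolerability conclusion changes; no dosing decision, stopping scenario, endpoint or SAP analysis does. The conclusion rests on taking the designation sentence at its word and on the ordinary meaning of MTD as a dose above which a higher one was not tolerated. The documents give no basis for saying how likely the affected outcomes are. Counting possible endings would not help either, since repeated, intermediate, reduced and higher doses are all allowed.

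**What to change.** Replace the designation sentence in Section 7.4.1 with:

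*An MTD will be designated, separately for single (Part A) and multiple (Part C) dosing, only if a higher dose level was judged not tolerated; it is then the highest tolerated dose level below that dose. Otherwise the MTD will be described as not reached, with the highest dose tested and the reason escalation ended.*

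The wording rests on a judgement about a dose level rather than on a stopping scenario having been met. The fourth scenario is confined to one dose level, but others are not; the second, for example, reads "2 subjects experience a clinically significant event of persistent tremors that is deemed to be related to LY3154885 administration" and could be met by events at different doses.

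The cost is two sentences in place of one. The downside is that the report may have to state that the MTD was not reached in Part A, Part C or both.

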7.5. Preparation/Handling/Storage/Accountability

The investigator or designee must confirm that appropriate temperature conditions have been maintained, as communicated by the sponsor, during transit for all investigational product received and that any discrepancies are reported and resolved before use of the study treatment.

Only participants enrolled in the study may receive IMP or study materials, and only authorized site staff may supply or administer IMP. All IMP should be stored in an environmentally controlled and monitored (manual or automated) area in accordance with the labeled storage conditions with access limited to the investigator and authorized site staff.

The investigator, institution, or the head of the medical institution (where applicable) is responsible for study treatment accountability, reconciliation, and record maintenance (such as receipt, reconciliation, and final disposition records).

7.6. Treatment Compliance

The IMP will be administered at the clinical site, and documentation of treatment administration will occur at the site.

7.7. Concomitant Therapy

Subjects on stable concomitant medication at the time of study entry should continue their regular, unchanged dose throughout the study. These permitted medications have been described in Exclusion Criterion [25].

In general, concomitant medication should be avoided; however, paracetamol/acetaminophen (1g, maximum 3g/24 hours) may be administered at the discretion of the investigator for treatment of headaches, etc. If the need for concomitant medication (other than acetaminophen) arises, inclusion or continuation of the subject in the study may be at the discretion of the investigator after consultation with a Lilly clinical pharmacologist. Drugs that are known inducers or inhibitors of CYP3A4 are specifically excluded. Any medication used during the course of the study must be documented.

